3. SAFETY ANALYSES

3.1 ADVERSE EVENTS

3.1.1 *Available data*

Adverse events (AEs) are coded into system organ classes and preferred terms using the medical dictionary for regulatory activities (MedDRA, see section 10.3). For each AE, start and stop date(time)s are collected as well as intensity, a seriousness flag, seriousness criteria, treatment-relationship, action taken towards the study treatment and outcome.

Immediate hypersensitivity reactions (IHRs) are collected in a dedicated eCRF and are coded according to MedDRA dictionary (see section 10.3). For each IHR, start and stop date(time)s are collected as well as associated signs/symptoms, severity and suspected anaphylaxis.

3.1.2 *Derivation rules*

Pre-treatment AEs are defined as AEs starting between date of informed consent with 00:00 added as time part and the date(time) of first study treatment administration – 1 minute, extremes included.

Treatment-emergent adverse events (TEAE) are defined as AEs starting on or after first administration of any study treatment.

Adverse drug reactions (ADRs) are defined as TEAEs related to study treatment or with missing relationship.

Based on their start date(time), AEs will be allocated to the phase during which they started. Phases are defined in section 6.2.1. In case the AE start date(time) is incomplete or missing and the AE could consequently be allocated to more than one phase, a worst-case allocation will be done as detailed below:

- Treatment phase vs. non-treatment phase: AE will be allocated to the treatment phase.

A fatal AE is defined as an AE with outcome 'fatal'.

An AE for which the study treatment was discontinued is defined as an AE with action taken 'drug permanently withdrawn'.

	Statistical Analysis Plan	
CLI-10067AA1-01	Final Analysis	Final 1.0 of 30MAY2024

AE onset and duration will be calculated as follows:

- AE onset day (vs. first administration) =
 - AE start date < date of first administration: AE start date – date of first administration
 - AE start date \geq date of first administration: AE start date – date of first administration + 1 day
- AE duration (rounded as detailed in section 6.3.4) =
 - If start and stop date(time)s are available:
 - AE end date(time) – AE start date(time) + 1 minute

Note: If AE duration is less than 1 hour, the duration will be presented in minutes. If the AE duration is 1 hour or more, but less than 1 day, it will be presented in hours. If AE duration is 1 day or more, it will be presented in days.

- If only start and stop dates are available:
 - AE end date – AE start date + 1 day
 - date of last contact – AE start date + 1 day (when the AE start date is fully known but the AE is not resolved at the end of the study); in this case the duration will be presented as “>x days”.

3.1.3 *Presentation of results*

Tables will present TEAEs and IHRs only. Pre-treatment AEs will only be listed.

An overview table will show the number and percentage of subjects with at least one event and the number of events by treatment for the following:

- TEAEs
- Serious TEAEs
- Non-serious TEAEs
- ADRs
- Serious ADRs
- Grade 3 or 4 TEAEs
- TEAEs leading to study treatment discontinuation
- TEAEs leading to death
- Immediate hypersensitivity reactions

Separate summary tables by MedDRA system organ class and preferred term will show the number and percentage of subjects with at least one event and the number of events by treatment for the aforementioned categories (except for IHRs). Each AE record in the clinical database is considered as a distinct adverse event and is counted as such. Blank system organ classes and preferred terms, if any, will be shown as ‘Not Available’ in the tables and listings.

All AEs, including pre-treatment events and all coding information will be listed. All IHR, including all reaction details will be listed. Separate listings will be prepared for the categories presented in the summary tables.

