7.1.2 Treatment period

The subject will attend ambulatory visits on Days 1, 2, 5, 7, 14, 28, 56, and 84 (end of study).

The following procedures will take place during the treatment period:

- SUBJECT SELECTION (**Day 1 visit**): Inclusion criteria no. [7](#) and exclusion criteria no. [1](#), [2](#), [12](#), [14](#), [18](#), [19](#), [27](#), and [32](#) will be re-checked as requested in [Sections 4.2](#) and [4.3](#). Subjects not fulfilling the mentioned criteria will be screen failed.
- RANDOMISATION (**Day 1 visit**): Subjects will be randomised to receive a single IV dose of CHF10067 or placebo.
- DOSING (**Day 1 visit**): Subjects will be administered a single IV dose of CHF10067 or placebo.
- PHYSICAL EXAMINATION (**Day 1, 2, 5, and 7 visits**): A full physical examination will be performed according to [Section 7.2.10](#) and any new revealed clinically significant abnormality since the last visit will be recorded as an AE.
- ABBREVIATED PHYSICAL EXAMINATION (**Day 14, 28, 56, and 84 visits**): A symptom-directed physical examination will be performed according to [Section 7.2.10](#) and any new revealed clinically significant abnormality since the last visit will be recorded as an AE.
- ADVERSE EVENTS RECORDING (**all visits**): Any new AE/SAE occurred since the last visit will be checked and recorded in the eCRF. The status of ongoing AEs will be checked and updated in the eCRF when applicable. Moreover, during this period in case of any new clinically significant abnormality revealed during the examination or procedures, it will be recorded as an AE.
- STUDY RESTRICTIONS (**all visits**): Study restrictions criteria will be checked according to [section 7.1.4](#).
- CONCOMITANT MEDICATIONS CHECK (**all visits**): Concomitant medications taken by the subject since the last visit will be checked and recorded in the eCRF.
- BLOOD TESTING: Blood sample collection for safety evaluations (clinical chemistry, haematology, fasting glucose [**Day 1 pre-dose, 2, 7, 14, 28, 56, and 84 visits**], immunogenicity [**Day 1 pre-dose, 14, 28, 56, and 84 visits**], and markers for evaluation of immediate hypersensitivity reactions [**Day 1 visit**]) according to [Sections 7.2.2.1](#),

Clinical Study Code No.: CLI-10067AA1-01	Version No.: 6.0
EUDRACT No.: 2022-001079-15	Date: 06 July 2023

7.2.2.4 and **7.2.2.5**. Subjects have to be in fasting condition from at least 10 hours before clinical chemistry and fasting glucose samples are collected.

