bias	The systematic tendency of any factors associated with the design, conduct, analysis and evaluation of the results of a clinical trial to make the estimate of a treatment effect deviate from its true value. Bias introduced through deviations in conduct is referred to as 'operational' bias. The other sources of bias listed above are referred to as 'statistical'.
case report form (CRF)	A printed, optical, or electronic document designed to record protocol required information to be reported to the sponsor for each trial subject.
display	Analysis table, listing or figure
missing data	Data that would be meaningful for the analysis of a given endpoint but were not collected. They should be distinguished from data that do not exist.
phase	Interval of time in the planned conduct of a study associated with a specific purpose: for example, screening, treatment, follow-up.
significant digit	All digits of a number used to express it to the required degree of accuracy, starting from the first non-zero digit.
standardised unit	unit populating --STRESU in the clinical database
treatment-emergent abnormality	Any postbaseline abnormality/toxicity that was not present at baseline (e.g., glucose low at baseline and high post-baseline; QTcF]450; 480] ms at baseline and >500 ms post-baseline)

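### TEAEs are defined by start date alone, so a screening-onset AE that worsens after infusion is left out of every TEAE-based table unless the worsening gets its own record, which the documents do not clearly require

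*SAP*

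**What the plan says.** SAP 3.1.2 gives the rule: "Treatment-emergent adverse events (TEAE) are defined as AEs starting on or after first administration of any study treatment". Phase allocation follows the same logic: "Based on their start date(time), AEs will be allocated to the phase during which they started". The one exception is for incomplete or missing start dates that leave the phase open: "Treatment phase vs. non-treatment phase: AE will be allocated to the treatment phase". ADRs are a subset: "Adverse drug reactions (ADRs) are defined as TEAEs related to study treatment or with missing relationship".

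SAP 3.1.3 then limits the output: "Tables will present TEAEs and IHRs only. Pre-treatment AEs will only be listed". The unit of counting is the record: "Each AE record in the clinical database is considered as a distinct adverse event and is counted as such".

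The protocol uses the term TEAE in 12.3.5.1 without defining it, and SAP 7.1 (changes to the planned analysis) does not mention it. On recording, protocol 7.1.2 asks sites to enter new AEs at each visit and says of existing ones: "The status of ongoing AEs will be checked and updated in the eCRF when applicable". Protocol 10.8 starts AE recording at consent. It also says that a change found at a later visit which the investigator judges clinically significant has to be entered as an AE.

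**The concern.** Safety and tolerability is the primary objective, and the AE tables are its main summary. Neither the SAP nor the protocol has a clause for worsening. If a screening-onset AE stays in one record, its start date remains before dosing whatever happens later. It could become severe, serious or fatal after the infusion and still appear only in a listing.

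Elsewhere the SAP treats change from a pre-existing state as emergent. Its definition of a treatment-emergent abnormality is "Any postbaseline abnormality/toxicity that was not present at baseline", and one of its examples is a QTcF already in the band above 450 and up to 480 ms at baseline that goes above 500 ms. SAP 2.2.3 counts pre-existing ADA boosted 4-fold or more towards ADA incidence. SAP 3.1.2 sends an AE of uncertain onset to the treatment phase as the worst case, but has no such provision for an AE known to have worsened after dosing.

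**Working it through.** The plan states no figure to reproduce on this point, so the check is mainly a trace of the rules.

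**Step 1. Can such records exist?** Yes. AEs are recorded from consent (protocol 10.8) and screening is 3 to 28 days before randomisation (protocol 7.1.1). Protocol 7.1.1 sends clinically significant findings at screening to medical history unless they began after consent and are not due to a pre-existing condition. The gap therefore concerns new AEs that start between consent and infusion, are still open at dosing, and then worsen.

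**Step 2. Where does each case end up?**

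| Case | Classification (SAP 3.1.2, 6.2.1) | Output (SAP 3.1.3) |
|---|---|---|
| Starts after dosing | TEAE | Tabulated |
| Starts in screening, worsens, kept as one record | Pre-treatment | Listing 16.2.7.1 only |
| Starts in screening, worsening entered as a new post-dose record | New record is a TEAE | Tabulated |
| Start date incomplete, phase uncertain | Treatment phase | Tabulated |
| Immediate hypersensitivity reaction (IHR) | Treatment phase | Own row in the overview table |

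Row 2 is missing from the overview table, from the tables by System Organ Class and Preferred Term for serious TEAEs, ADRs, grade 3 or 4 TEAEs and TEAEs leading to death, and from the summary by ADA status. All of these are built on TEAEs.

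**Step 3. Which of rows 2 and 3 applies?** Protocol 7.1.2 treats new AEs and ongoing AEs as two separate actions, and only the status of ongoing ones is updated. That leans towards row 2. Protocol 10.8 could lead to row 3, but it does not say that an AE already on record and now worse needs a second record. The data fields in SAP 3.1.1 include start, stop and intensity, but no date of a change in intensity. From those fields alone, the analysis could not recover a worsening held inside one record.

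**Step 4. How much does one omitted subject weigh?** Inputs from protocol 12.1: 6 active and 2 placebo per cohort, 3 cohorts. Active = 3 × 6 = 18; placebo = 3 × 2 = 6; total = 24.

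- Dose group: 1/6 = 16.7 points. A row moves from 0/6 (exact Clopper-Pearson 95% CI 0 to 45.9%) to 1/6 (0.4 to 64.1%).
- Pooled active: 1/18 = 5.6 points. A row moves from 0/18 (0 to 18.5%) to 1/18 (0.1 to 27.3%).

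**Step 5. How likely is at least one?** The documents give no rate. Assuming a per-subject probability q, independent between subjects, the chance of at least one is 1 − (1 − q)^n:

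| Assumed q | n = 18 active | n = 24 all |
|---|---|---|
| 2% | 30% | 38% |
| 5% | 60% | 71% |
| 10% | 85% | 92% |

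These rows show only how the answer depends on q; none of them is an estimate.

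**The case against.** A reader might infer that a worsened screening event can never reach a safety table. The documents do not support that. Protocol 10.8 offers a plausible route to a post-dose record, and such a record would be counted. IHRs have their own form and their own row. Measured worsening in laboratory values, vital signs, oxygen saturation, ECG and lung function appears in the tables for those parameters.

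A reader might also take protocol 7.1.2 as proof that grade is overwritten in place. It says only that status is updated, which may mean resolution or outcome. The convention may well be set in eCRF guidance that is not part of these documents.

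Third, it is tempting to cite chronic IPF cough or dyspnoea as the typical missed event. Under protocol 7.1.1 these are normally medical history, so a post-dose aggravation reported as an AE would be a first record with a post-dose start, and hence a TEAE. The Day 1 rechecks also remove some subjects with events open at dosing, such as current infection or acute exacerbation.

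The inconsistency argument has limits too. Treatment-emergent abnormality is a separate term, illustrated with measured parameters, so the comparison shows a difference of approach rather than a contradiction.

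Finally, all AEs are listed, 24 subjects can be read by eye, and the escalation stopping rules in protocol 6.2.2.1 are worded in AEs and SAEs, so the TEAE definition does not touch them.

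All of this narrows the point. None of it supplies a worsening clause or a clear requirement for a new record.

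**Conclusion.** The point holds in a limited form. Under SAP 3.1.2 and 3.1.3, an AE that starts between consent and infusion and worsens in grade or seriousness after dosing is absent from every TEAE-derived table unless the worsening is a separate record. Whether it becomes one is left open.

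The possible error is an undercount. The figures of 16.7 and 5.6 points are the most that one omitted subject can contribute to a row. The any-TEAE row does not move if that subject has another TEAE during follow-up. The sparse rows (serious, grade 3 or 4, death) are more exposed, because one subject may be the whole entry. The rule applies to active and placebo alike, so the documents do not establish a direction of bias in the comparison between them. They also give no basis for saying how often such events occur. The data are not lost; the weakness is in what is counted.

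**What to change.** 1. **SAP 3.1.2.** Define a TEAE as an AE that starts, or worsens in CTCAE grade or seriousness, on or after first administration. Apply this to all TEAE-derived tables, including ADRs, serious and grade 3 or 4 events, deaths and the ADA-status summary.
2. **eCRF guidance.** State that post-dose worsening of a screening-onset AE is entered as a new record with its own start date and time, and that the original record is closed at its pre-dose grade. Without this the new clause cannot be derived, because no date of grade change is among the listed fields. Closing the original record also prevents double counting, since every record counts as an event.
3. **If data are already collected.** Review the pre-treatment AEs (the content of Listing 16.2.7.1) at the data review meeting, before unblinding. Document in the data review report any that worsened after dosing and are to be counted as TEAEs.

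The cost is an amended SAP definition, an eCRF completion note and a little extra data review. No design figure changes.

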2.0	25 August 2022	
Protocol version 2.0 (dated 25 August 2022) incorporated the following changes into protocol version 1.0 (dated 03 May 2022) based on Medicines and Healthcare products Regulatory Agency (MHRA) feedback:
 
 Section 6.2.2.1 Dose escalation stopping rule was updated: ‘Three or more subjects on active drug* experience a severe, possibly drug-related AE lasting for > 24 hours duration’ is replaced by ‘two or more subjects on active drug* experience a severe, possibly drug-related AE lasting for > 24 hours duration’. Section 10.3 Intensity of Adverse Event was amended so that the Common Terminology Criteria for Adverse Events (CTCAE) would be used as the adverse event severity grading scale rather than a 3-point severity grading scale with CTCAE. Section 12.3.5.1 Adverse Events was amended to change the statistical analysis so that treatment-emergent adverse event data will be summarised by CTCAE grade rather than severe intensity.
3.0	24 October 2022	
 See the list of substantial changes in the summary of changes dd 24 October 2022.
4.0	22 May 2023	
Protocol version 4.0 (dated 22 May 2023) removed the bronchoscopy procedure from protocol version 3.0 (dated 24 October 2022) based on MHRA feedback in the following sections:
 
 Section 1.3 Risk/Benefit Assessment Section 4.1 Subject Recruitment Section 7.1 Study Schedule – All Cohorts Section 7.1.2 Optional Additional Visit for Bronchoscopy

Clinical Study Code No.: CLI-10067AA1-01	Version No.: 6.0
EUDRACT No.: 2022-001079-15	Date: 06 July 2023

		
• Section 7.2.12 Optional Bronchoscopy for Bronchoalveolar Lavage and Bronchoabsorption Assessment• Section 25 References
5.0	16 June 2023	See the list of the substantial changes in the Summary of Changes dated 16 June 2023.
6.0	06 July 2023	Non substantial changes to correct inconsistencies related to the timing of vital signs and oxygen saturation assessments: 
• Section 7.1 Footnotes for Evaluation Schedule• Section 7.2.7.3 Oxygen Saturation• Section 7.2.8 Vital Signs.

Clinical Study Code No.: CLI-10067AA1-01	Version No.: 6.0
EUDRACT No.: 2022-001079-15	Date: 06 July 2023

PROTOCOL OUTLINE

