10.3 Intensity of Adverse Event

For the classification of AEs severity (except for immediate hypersensitivity reactions severity, see below), the Common Terminology Criteria for Adverse Events (CTCAE) [23] will be used:

- Grade 1 Mild; asymptomatic or mild symptoms; clinical or diagnostic observations only; intervention not indicated.
- Grade 2 Moderate; minimal, local, or noninvasive intervention indicated; limiting age-appropriate instrumental Activities of Daily Living (ADL)*.
- Grade 3 Severe or medically significant but not immediately life-threatening; hospitalization or prolongation of hospitalization indicated; disabling; limiting self-care Activities of Daily Living**.
- Grade 4 Life-threatening consequences; urgent intervention indicated.
- Grade 5 Death related to AE.

*Instrumental ADL refer to preparing meals, shopping for groceries or clothes, using the telephone, managing money, etc.

**Self-care ADL refer to bathing, dressing and undressing, feeding self, using the toilet, taking medications, and not bedridden.

In order to guarantee objectivity and consistency in the evaluation of AEs (including classification of severity), the proposed guidance should be followed in alignment with best medical practice.

Laboratory abnormalities and other clinical assessments (e.g., 12-lead ECG) will be reported as AEs if judged by the Investigator as being clinically significant.

In case of laboratory evaluations or other clinical assessments (e.g., 12 -lead ECG) not listed in the CTCAE grading table, the AE severity will be judged by the Investigator based on the local ranges.

Taking into consideration the disease examined in the current study, it should be acknowledged that the guidance may not always be applied. Therefore, although the guidance should be followed, whenever possible, in order to ensure an accurate and objective evaluation of the AEs, the final decision on the severity classification remains the responsibility of the Investigator.

For the specific classification of severity and management of immediate hypersensitivity reactions, refer to [Section 7.2.2.5.1](#).

Clinical Study Code No.: CLI-10067AA1-01	Version No.: 6.0
EUDRACT No.: 2022-001079-15	Date: 06 July 2023

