12.3.5.1 Adverse events

The number of events and the number and percentage of subjects experiencing treatment emergent-adverse events (TEAEs), treatment-emergent ADRs, serious TEAEs, non-serious TEAEs, TEAEs by CTCAE grade, TEAEs leading to discontinuation of study drug and TEAEs leading to death will be presented by treatment. The aforementioned categories of AEs will be also summarised by System Organ Class and Preferred Term using the MedDRA dictionary.

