14.2.2.2	CHF10067 Serum Concentrations (ng/mL) by Scheduled Time (PK Set) Individual values and descriptive statistics of CHF10067 serum concentrations per dose level	PK	PCT002
14.2.2.3	CHF10067 Serum PK Parameters (PK Set) Individual values and descriptive statistics of CHF10067 serum PK parameters, per dose level	PK	PKT001
14.2.2.4	Dose Proportionality Assessment of CHF10067 Serum PK Parameters (Power Model) (PK Set) The slope and 90% CI of the power model will be tabulated by PK parameter of CHF10067 (AUC _{0-t} , AUC _{inf} , and C _{max})	PK	
IMMUNOGENICITY			
14.2.4.1	Summary of ADA Responses (Safety Set) [KFR] Tabulation of the number and percentage of subjects as classified in section 2.2.3.	SAF	
14.2.4.2	Summary of TEAEs by Subject ADA Status (Safety Set) Tabulation of the number and percentage of subjects with at least one TEAE by subject ADA status (ADA+ or ADA-). Note: if the number of ADA+ subjects is less than 3, this table will be generated without results. Instead, an informative message will be printed in this output.	SAF	AET001
SAFETY			
ADVERSE EVENTS			
14.3.1.1	Summary of TEAEs (Safety Set) [KFR] Tabulation of the number and percentage of subjects with at least one of the events described in the SAP. The number of events will also be shown.	SAF	AET001
14.3.1.2	TEAEs by System Organ Class and Preferred Term (Safety Set) Tabulation of the number and percentage of subjects with TEAEs by MedDRA system organ class and preferred term. The number of events will also be shown.	SAF	AET003

	Statistical Analysis Plan		
CLI-10067AA1-01	Final Analysis	Final 1.0	of 30MAY2024

Number	Title	Analysis Set	TLFs Library Template Number
14.3.1.3	Serious TEAEs by System Organ Class and Preferred Term (Safety Set) Tabulation of the number and percentage of subjects with serious TEAEs by MedDRA system organ class and preferred term. The number of events will also be shown.	SAF	AET003
14.3.1.4	Non-Serious TEAEs by System Organ Class and Preferred Term (Safety Set) Tabulation of the number and percentage of subjects with non-serious TEAEs by MedDRA system organ class and preferred term. The number of events will also be shown.	SAF	AET003
14.3.1.5	ADRs by System Organ Class and Preferred Term (Safety Set) [KFR] Tabulation of the number and percentage of subjects with ADRs by MedDRA system organ class and preferred term. The number of events will also be shown.	SAF	AET003

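### The SAP replaces the protocol's adverse-event summary by CTCAE grade with one pooled grade 3–4 category and does not record the change

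*SAP*

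**What the plan says.** Protocol 12.3.5.1 specifies the measures, "The number of events and the number and percentage of subjects experiencing treatment emergent-adverse events (TEAEs"), and then names the categories they apply to. One of these is severity: "TEAEs by CTCAE grade, TEAEs leading to discontinuation of study drug and TEAEs leading to death will be presented by treatment". It adds: "The aforementioned categories of AEs will be also summarised by System Organ Class and Preferred Term using the MedDRA dictionary". The by-grade summary is therefore required both overall and by system organ class and preferred term.

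Protocol 10.3 adopts CTCAE and defines grades 1 to 5. Grade 2 is a distinct level: "Grade 2 Moderate; minimal, local, or noninvasive intervention indicated". Immediate hypersensitivity reactions are carved out of that scale ("except for immediate hypersensitivity reactions severity, see below") and graded mild, moderate or severe under Protocol 7.2.2.5.1.

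SAP 3.1.3 lists the rows of the adverse-event overview. The only row based on grade is "Grade 3 or 4 TEAEs"; TEAEs leading to death have a separate row. In SAP 9.1, overview Table 14.3.1.1 takes its content from that list ("Tabulation of the number and percentage of subjects with at least one of the events described in the SAP"), and Table 14.3.1.7 is restricted to grade 3 or 4. In SAP 9.2, Listing 16.2.7.7 has the same restriction.

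**The concern.** A summary by grade is a breakdown over the whole scale. A grade 3–4 row is one threshold on it, and is not a reasonable reading of the protocol text. The current wording of Protocol 12.3.5.1 settles this alone. The version 2.0 entry in the protocol's version history agrees with it and gives context: the section was amended so that "treatment-emergent adverse event data will be summarised by CTCAE grade rather than severe intensity". A single high-severity row moves back towards the form that was replaced.

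The study is descriptive, with no formal power calculation, and its primary objective is safety and tolerability, so the summary tables are the primary analysis. If events are mostly mild or moderate, the question of interest is whether moderate events become more frequent with dose or relative to placebo. The planned severity rows cannot show that.

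The departure is also undocumented. A reader who relies on SAP 7.1 to learn what changed would not find it.

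**Working it through.** The plan gives no figure to reproduce. The check sets the texts side by side and then counts what the planned rows can distinguish.

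**1. Coverage of the scale**

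| CTCAE grade (Protocol 10.3) | Protocol 12.3.5.1 | Severity rows in SAP 3.1.3 and Table 14.3.1.7 |
|---|---|---|
| 1 | shown | none |
| 2 | shown | none |
| 3 | shown | pooled with 4 |
| 4 | shown | pooled with 3 |
| 5 | shown | in practice, through the death row |

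Five grades become one pooled row plus the death row. No other table in SAP 9.1 shows TEAEs by individual grade.

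**2. Is the change recorded?** SAP 7.1 has six entries: immunogenicity, oxygen saturation plots, lung function, placebo-corrected ECG change, TG2 in healthy subjects, and the by-dose-level wording. Entries on adverse events: 0. The section records changes as small as adding individual oxygen saturation plots. It also records that two protocol immunogenicity tables became a listing, which is the same kind of change as leaving grade detail only in a listing.

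**3. What the rows cannot distinguish**

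- Group size: 6 on each active dose (Protocol 12.1). Pooled placebo (SAP 6.4.2) is also planned as 3 cohorts × 2 = 6.
- Let n be the number of subjects in a group with at least one TEAE, and suppose none reaches grade 3.
- The three rows then read n (any TEAE), 0 (grade 3 or 4) and 0 (death).
- The number of subjects with at least one grade 2 TEAE, a count the protocol asks for, can be 0, 1, …, n. That is n + 1 possible values.

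| n | possible numbers of subjects with a grade 2 TEAE |
|---|---|
| 1 | 2 |
| 2 | 3 |
| 3 | 4 |
| 4 | 5 |
| 5 | 6 |
| 6 | 7 |

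The three rows are identical for every value on a line. The values of n are an assumed range, not a forecast.

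**4. Events.** In the same scenario the combined number of grade 1 and 2 events equals the total number of TEAEs, but its split by grade is not shown. When severe or fatal events do occur, the combined number is the total minus grade 3–4 minus fatal events. This holds only if every record carries a CTCAE grade and every fatal event is graded 5. SAP 3.1.2 defines a fatal event by outcome, so that match is an assumption.

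**The case against.** The strongest reply is that little is lost in practice. The study has 24 subjects, intensity is collected for every adverse event (SAP 3.1.1), and Listing 16.2.7.2 shows all the adverse-event information. A reader could count grades by group by hand. No estimate or test is biased, and escalation is decided on interim safety reports under a separate charter, not on these tables. All of this stands, and it limits the weight of the point. It does not remove the point: the protocol asks for counts and percentages by treatment and by system organ class and preferred term, and a listing does not provide them.

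The n + 1 count can be called generic, since it arises whenever two categories are merged. That is fair. It describes ambiguity in three table rows, not in the full set of outputs, and the comparison of rows would be enough without it.

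The version history can be read as recording only a change of scale. The conclusion does not need it, because the current Protocol 12.3.5.1 is explicit.

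Protocol 12.3 leaves detail to the SAP. That allows the SAP to elaborate a named summary, not to drop it without saying so.

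The protocol does not itself ask for a by-grade listing, and hypersensitivity grading is a side issue. Both are true. The listing change follows only from SAP 3.1.3's own rule that each tabulated category has a listing, and the hypersensitivity sentence is a secondary clarification.

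**Conclusion.** The concern holds and should be fixed. The SAP contradicts the protocol's severity summary for the primary objective, and SAP 7.1 does not record the departure. Five grades are reduced to one pooled row plus the death row. In a group of 6 with no event at grade 3 or above, the rows leave up to seven possible values for the number of subjects with a grade 2 event. That figure assumes all 6 have a TEAE; with fewer it is n + 1. The effect is confined to the planned final safety tables. The underlying data, the full listing and the dose-escalation process are not affected.

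**What to change.** In SAP 3.1.3 and Table 14.3.1.7, present TEAEs for each CTCAE grade from 1 to 5, giving events and subjects with percentages, by treatment, overall and by system organ class and preferred term. Align Listing 16.2.7.7 with the revised table. Counting each subject once at the highest grade is a sensible convention, though the protocol does not require it. The pooled grade 3–4 row can stay as an additional line.

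If the sponsor prefers the pooled category alone, SAP 7.1 needs an entry that records and justifies it.

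One further sentence would help: state how an adverse-event record linked to an immediate hypersensitivity reaction is placed in the grade table. Protocol 10.3 takes those reactions out of CTCAE, while SAP 3.1.3 counts every adverse-event record.

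The cost is SAP wording, extra rows in two tables and one adjusted listing, or else a single SAP 7.1 entry. All of it uses intensity data already collected.
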